## 5. STUDY INTERVENTIONS

**Figure 3. M-ROCC Group Outlines**

### 5.1 Interventions, Administration, and Duration

Interventions: *Live-Online M-ROCC, the Mindful Recovery OUD Care Continuum*

While the 8-week MBI standard has been helpful for research reproducibility, it often can lead participants with OUD to feel overwhelmed by practice expectations, unintentionally causing self-judgment and shame, leading to relapse. For others, just as mindfulness begins to click for them at 8 weeks, the program ends. For this reason, M-ROCC is stage-oriented and motivationally-responsive. M-ROCC (Fig.3) meets participants where they are. The introductory low-dose mindfulness group (LDM) is the first stage and it is designed to foster engagement, reduce stress, introduce skills for autonomic regulation, and provide a non-judgmental group environment, exposing participants to mindfulness and self-compassion with a 4-week minimum commitment. The LDM group uses rotating short modules in 50-minute sessions for 4-8 weeks with short mindfulness practices, experiential exercises, recordings, and introduction to free online mindfulness resources, with demonstrated feasibility to integrate into addiction treatment. M-ROCC allows people to repeat the 4-week LDM group as needed as they work with the ascending practice dose ladder and become ready for the intensive group, working to build confidence, safety, self-efficacy, and enhance motivation for mindfulness and recovery. After completion of LDM, participants are encouraged to start an intensive group (MTPC-OUD) of 6-15 people. If at least 8 people are ready to transition to an intensive group after 4 weeks then the group will be able to do so. Those who are not ready to transition when the majority of the group transition at either 4 or 8 weeks, can transition to another LDM group at another time if they would like to do so. Participants will join an MTPC-OUD group for 16-weekly 90 minute sessions, which are designed to enhance self-regulation, integrate mindfulness for living well through stress, anxiety, depression, pain and addiction recovery, create an experience of common humanity, and learn from each other's experiences. The 16-week MTPC-OUD group is designed to minimize scheduling difficulties on behalf of both patients and providers, and to increase feasibility in primary care settings where scheduling a longer group may be challenging. Whereas the LDM group is designed to introduce participants to mindfulness practice in an accessible and motivational manner, the MTPC-OUD group is more similar in content to an intensive 8-week MBIs in terms of practice and content. Participants are asked to engage in longer practices (~30 minutes) designed to address more complex topics such as self-compassion, self-management for chronic illnesses, and skills for addressing cognitive patterns of worry and rumination that could otherwise overwhelm novice meditators. After completion of MTPC-OUD, participants can go to a mindfulness maintenance (MCS) group, available in the form of CMC's weekly free live online mindful recovery addiction maintenance community group. This group will run for 60 minutes, and will begin with a longer mindfulness practice followed by a brief inquiry, a brief recovery check-in, and concluding with a shorter mindfulness practice. MCS groups may also be available in the wider community. These groups are flexible in terms of delivery, provided they meet the requirements to be considered an MCS group (mindfulness practice, inquiry and discussion, group check-in). Participants will be given

the option to participate in one of these groups in order to strengthen their practice, however community groups will not be considered to be part of the study or the M-ROCC curriculum. M-ROCC's key focus on autonomy, collaboration and naturalistic selection to different levels based on readiness reduces unnecessary attrition and decreases the likelihood of participants feeling shame or failure if they fail to attain higher levels of practice.

Importantly, due to the impact of COVID-19 all M-ROCC groups will take place online via HIPAA compliant Zoom software. Each M-ROCC group will start with a 15-30 minute live-online check-in period. During this time, participants will be able to meet together in groups of three to discuss their week and experience with mindfulness practices. This brief group is designed to foster interpersonal connection in an online setting where it may otherwise be difficult for participants to interact. Each week we will randomly select 3-6 individuals who will conduct supervised oral fluid toxicology tests during this check-in period with study staff in a private Zoom breakout room. The study team will aim to supervise oral fluid testing among participants once every 2 weeks. If participants do not show up for group but they were randomly selected, then they will be expected to meet within 24 hours with study staff by video to conduct the online screening test.

**The Mindful Recovery Opioid Care Continuum (M-ROCC) integrates an ascending practice dose ladder across the 3 group stages.** This slow and focused approach to developing home practice differs from standard MBIs which expect static high levels of practice throughout. In a previous pilot of an 8-week MBI group for OUD, participants reported feeling discouraged, overwhelmed, guilty, and that it moved too fast to learn and remember the multiplicity of skills taught each week. More time was needed to develop mindfulness practice confidence, which is important because mindfulness practice dose is associated with the amount of neurophysiologic change people experience during MBIs (e.g., attention/inhibitory control).

The ascending practice dose ladder, which is introduced in the LDM group, provides steady encouragement to increase mindfulness of breathing by an average of 5 minutes of practice per week, building up to 20 minutes a day, providing validation for any practice they are doing, building confidence and self-efficacy. Once the participant begins the MTPC-OUD group they will therefore have an existing mindfulness practice, which will allow them to engage in longer 30-minute practices without being overwhelmed. If the program moves too fast with unrealistic expectations at the outset, then self-stigma, self-criticism, regret, and avoidance can lead to dropout, which has more substantial clinical implications in OUD treatment (relapse, overdose) than in standard MBIs for other diagnoses, where completion rates are often around 50%. In the M-ROCC R21

pilot, one participant stated the most important part of the LDM group was “going from 5 minutes to 15 minutes a day of practice”. **In this way, a stage-oriented continuum of care holds promise to impact OUD outcomes.**

### **Comparator (Live-Online Control) Design:**

This randomized controlled trial will employ an attention- and time-matched live online control group as a standalone comparator intervention. In a similar manner to the M-ROCC check-in group, this weekly control group will offer participants the ability to connect in groups and discuss the challenges that they are facing online with each other. This approach allows for participants to connect in a manner that they would not otherwise be able to, considering that the majority of B/N prescription sites are not offering in-person groups as a result of the COVID-19 pandemic. After completion of the testing and check-in groups, the full group will come together for a 45-60-minute check-in as a group. As an active group comparator, this method will help to isolate mindfulness aspects by controlling for the therapeutic aspects of group and will match the toxicology screening methods across groups as well. Group content will derive from commonly used methods in community substance use disorder programs and recovery groups, including an eclectic curriculum designed to emulate common curricular elements, with representation from commonly implemented evidence-based approaches (Motivational Interviewing, CBT, Community Reinforcement and Twelve Step Facilitation), using engagement and group building processes commonly used in addiction community groups. The manualized group will be standardized across each control group to ensure low variability across cohorts, starting with group check-in and then presentation of a skill and/or discussion of a topic.

### Administration

Participants will be enrolled on a rolling basis in preparation for their randomization to either the live-online M-ROCC or live-online control arm. Initially, randomization will only occur once 24 patients are ready for randomization. Following this initial group, every 4 weeks if at least 24 participants have completed baseline measures and are ready to start a group, they will be randomized using randomly selected block sizes of 4, 6 and 8 with a 1:1 ratio (24 weeks of live online M-ROCC : 24 weeks of live online control group). Next, after randomization, the participant will be informed about their assignment and given a start week for group sessions (either live online control or live online M-ROCC LDM) and will be given information about the group and its structure with a start date scheduled. We will aim to recruit constantly, with a new M-ROCC and control group beginning every 4-5 weeks.

We will aim for participants to begin attending control or LDM groups as soon as possible after randomization, but at least within 4 weeks. The study timeline will start

with week 1 being the first week the participant is assigned to start the study assigned group. Participants will continue to participate in standard care at each site while awaiting randomization and group placement, as well as throughout their enrollment in the study. For both study arms, participants will verify their presence with the group leader or research coordinator who will take attendance each week, which will be transferred to REDCap by the research coordinator after group.

After completion of the rigorous RCT consisting of 4-8 weeks of low dose mindfulness (LDM), LDM participants will be encouraged to proceed after LDM into the remainder of the M-ROCC program with a naturalistic design to evaluate the choices and outcomes that OUD participants make when engaging in additional mindfulness training (MTPC-OUD) and MCS sessions. After completion of LDM, participants may repeat with multiple cycles of LDM or may enter the next MTPC-OUD group. The availability of MTPC-OUD groups will depend on the number of group participants interested. Intensive mindfulness group-based intervention will be scheduled after 8 participants are willing to transition to intensive, but can only start when there is a critical mass greater than 6 participants to maintain the synergistic container effects important to the mindfulness group approach, such as common humanity and learning from each other's experiences.

MTPC-OUD intensive groups will run every 1-2 months and MCS groups will be run continuously in the form of free live online addiction mindful recovery groups. The CMC Free Live Online addiction recovery group led by the M-ROCC clinical director is a live-online group (<https://www.chacmc.org/connect>) following the MCS curriculum, which can be accessible by Zoom for anyone, and would be available for any study participant who has completed an MTPC-OUD group, or who is not comfortable moving from their LDM group to an MTPC-OUD group.

We anticipate about half of the M-ROCC sample will choose to initiate MTPC-OUD within the first 8 weeks. This is based on our having 9 out of 18 people who enrolled in the LDM in our initial pilot site choose to participate in MTPC-OUD.

M-ROCC participants may join the MCS or the intensive MTPC for the remainder of the study according to their choice. In the pilot study, 2 out of 18 people who started M-ROCC chose to return to a standard group-based opioid treatment (GBOT) level of care and 2 transitioned to individual therapy. Given the risk of overdose in this population, after 4 weeks of LDM, if a participant in M-ROCC chooses to leave the M-ROCC group and return to another level of care (perhaps because of schedule or change in risk level), then we believe it is imperative that we allow them to do that to avoid risk of harm. This is part of the naturalistic design and data on switching will be collected.

The LDM and MTPC group sessions will not be billed to insurance as group

psychotherapy or shared medical visits and no-co-pays will be collected. These will be run as research groups – this will be outlined in the consent form. Participants will be required to remain in their existing BUP treatment program in addition to being randomized to either study arm. MCS groups will be 50 minute groups that participants will be able to join after the study, if the study group ends at 20 weeks for them, or if they decide not to do the live-online intensive MTPC-OD program. Free MCS groups will be available through the CMC Free Live Online Community Program.

#### Duration

Participants will complete study procedures for a total of 24 weeks. Participants will be asked to make a live-online group commitment for at least 4 weeks (attending groups once a week), after which they will be encouraged to attend weekly groups for 16 additional weeks. Since group participants will be referred from multiple different sites, the importance is that the requirement is the same across both study arms.

If a participant is in the MTPC-OD group at week 24, then they will still complete the week 24 assessments within the 2-week completion window even though they have not completed the MTPC-OD group.

Any assessment battery (specifically online surveys not including oral fluid screens) completed more than 2 weeks after it is expected to be completed by the study timeline would be marked as outside the acceptable assessment window and excluded from primary analyses. Sensitivity analyses for late survey data collected outside this time window will be conducted and if it does not differ than it may be considered for inclusion in analyses.

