#### 6.2.3 Blinding

See Table 2 for blinding status for study staff. Participants will not be blinded to their assigned study arm (M-ROCC vs. control), nor will the research coordinators, data analyst, or methodologists. The PI will be blinded to assigned study arm when reviewing data quality, adverse events, protocol violations, etc.

Table 2. Blinding Status of Study Staff

Study Role	Blinding Status	Time of unblinding
------------	-----------------	--------------------

PI	Blinded	When all primary outcome data have been collected and when database is locked
Data Analyst ([name], [name], [name])	Not Blinded	Will prepare reports for DSMB with unblinded data, but will not have contact with participants.
Methodologists ([name]/[name])	Not Blinded	Will review reports for DSMB with unblinded data, but will not have contact with participants.
RCs	Not blinded	
Clinical/Medical Directors	Not blinded	
Participants	Not blinded	

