## **9.5 Outcomes**

### **9.5.1 Primary Outcome**

Biochemically-confirmed opioid abstinence, which is defined as the number of two-week periods with a negative oral fluid test [negative for opiate, oxycodone, fentanyl, methadone] AND no self-reported illicit opioid use, based on weekly substance use self-report during the final 12 weeks (weeks 13-24) of the study (6 is the highest possible number of negative oral fluid toxicology screen time periods). Participants will be randomly selected to undergo a live-online supervised oral fluid screen at a rate of once every 2 weeks. Negative toxicology screens have been previously used to assess effectiveness of OUD treatment.

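### Late survey batteries are excluded but may be let back in on an undefined no-difference check, so the dataset for PROMIS anxiety and pain interference depends on the data

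*Combined protocol and SAP*

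**What the plan says.** The rule is in section 5.1 under Duration. It applies to any survey battery "completed more than 2 weeks after it is expected to be completed by the study timeline"; such a battery "would be marked as outside the acceptable assessment window and excluded from primary analyses". Its scope is given as "specifically online surveys not including oral fluid screens".

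The following sentence reopens the exclusion. "Sensitivity analyses for late survey data collected outside this time window will be conducted", and then: "if it does not differ than it may be considered for inclusion in analyses".

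Other sections that bear on this:

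- Section 6.2.5 repeats a two-week window for the week 24 session and says nothing more about late data.
- Section 9.6 sets out mixed models and multiple imputation for the PROMIS outcomes. It does not mention late batteries or say whether an excluded late value counts as missing.
- Section 6.2.3 says participants are not blinded, "nor will the research coordinators, data analyst, or methodologists". Table 2 keeps the PI blinded until the primary outcome data are collected and the database is locked.
- Section 9.5.1 builds half of the primary outcome on self-report, "based on weekly substance use self-report during the final 12 weeks". The weekly survey that supplies it is an online survey, listed in section 10.1 under the clinical assessment battery.

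**The concern.** An exclusion rule protects the analysis only if it is settled before the results are known. Here the exclusion is provisional. Late data can re-enter after someone has examined them, and re-entry is permitted rather than required.

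The condition for re-entry has no content that could be checked later. The plan does not say whether late responses are compared with on-time responses or treatment effects are compared with and without late data. It gives no test or margin, and does not say who decides or when. Nor does it say which analyses would change.

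The outcomes mainly affected are PROMIS anxiety and PROMIS pain interference at 24 weeks, two of the four main secondary outcomes, and the exploratory questionnaires. For these, two defensible datasets would exist at the time of analysis and the plan does not say which one counts.

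**Working it through.** **Plan's own figures.** The documents give no number for the late-survey rule, so there is none to reproduce on this point. The sample-size figures in section 9.2 serve only to set the arm size:

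- Design effect = 1 + (24 − 1) × 0.01 = 1.23. Effective sample = 192 / 1.23 = 156.1, or 78 per arm.
- Pooled SD = √[(1.23² + 1.27²)/2] = 1.250. d = (4.67 − 4.11)/1.250 = 0.448.
- Power for d = 0.45 with 78 per arm, two-sided 0.05: 80.2% (normal approximation) or 79.7% (noncentral t). The plan's figures reproduce.

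**Type I error under different readings.** Assumptions: no treatment effect, one normally distributed outcome, 78 per arm, two-sided 0.05 t-test, equal late share in both arms, 40,000 simulated trials per row. Late shares of 5–30% are assumed because the documents state none. The check is read as a non-significant difference in treatment effect between late and on-time batteries.

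| Late share | In-window only, fixed | All data, fixed | Automatic inclusion after check | Free choice after check | Free choice, no check | Datasets disagree on significance |
|---|---|---|---|---|---|---|
| 5% | 5.0% | 4.9% | 5.1% | 6.0% | 6.1% | 2.2% |
| 10% | 4.7% | 4.8% | 5.0% | 6.1% | 6.2% | 3.0% |
| 20% | 5.0% | 4.8% | 5.4% | 6.9% | 7.0% | 4.2% |
| 30% | 4.9% | 4.9% | 5.8% | 7.4% | 7.5% | 5.1% |

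Simulation standard error near 5% is √(0.05 × 0.95 / 40,000) = 0.11 points. With 96 per arm, free choice after the check gives 5.9%, 6.2%, 6.9% and 7.4%. A repeat at 78 per arm gave about 6.0%, 6.5%, 7.3% and 7.5%, whether the check compares treatment effects or late with on-time responses.

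If no difference means that both datasets must reach the same significance verdict, there is no inflation: late data then enter only when the verdict equals the in-window one, so the error rate is that of the in-window analysis.

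**How informative the check is.** Take a true late versus on-time difference in treatment effect of 0.56 SD (an illustrative value). With n_L late and n_O on-time per arm, SE = √(2/n_L + 2/n_O) and power = Φ(0.56/SE − 1.96) + Φ(−0.56/SE − 1.96).

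| Late share | n_L, n_O per arm | SE | Power |
|---|---|---|---|
| 5% | 4, 74 | 0.726 | 12% |
| 10% | 8, 70 | 0.528 | 19% |
| 20% | 16, 62 | 0.397 | 29% |
| 30% | 23, 55 | 0.351 | 36% |

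The check would usually be passed even with a difference of that size. For anxiety, section 9.6 restricts the analysis to participants with baseline T-scores above 55, so at a given late share the late group is smaller still.

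**The case against.** The strongest reply is that the sentence does not say what the worst reading needs. The subject of its condition is an ambiguous pronoun that most naturally points to the late survey data. The comparison may therefore be of late with on-time responses, not of two treatment effects, and re-entry into analyses need not mean replacing the main one. A reader might infer that the plan lets the analyst see both results and report the better; the text does not say so. This stands as a limit on wording. It does not rescue the rule, because either comparison depends on the data and the decision is still discretionary.

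The size is also open to challenge. Strict readings give about 5%. The late share may be low: the window is two weeks, section 6.2.5 pays a bonus for completing batteries within 48 hours, and staff call participants every two weeks. At 5% late, free choice after the check costs about one point. The simulation also uses a single outcome with a t-test, whereas section 9.6 plans repeated-measures mixed models with imputation; using weeks 8 and 16 should make the two datasets agree more and shrink the inflation. All of this stands.

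A reader might also infer that the rule defeats the false discovery rate procedure. That was not calculated and is not claimed. Finally, unblinding adds little once the database is locked. This is largely fair: the main fault is lack of prespecification, and unblinding only removes a possible safeguard.

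**Conclusion.** The concern holds as a modest but real fault. The plan states a data-dependent, discretionary rule for choosing the dataset, and section 9.6 does not settle it.

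For one survey outcome, with late shares assumed at 5–30%, type I error is about 5.0–5.8% if inclusion is automatic after a non-significant check, 5% if both datasets must agree on significance, and about 6–7.5% if either dataset may be reported after the check. The excess is thus between nil and about 2.5 points, depending on a reading the plan leaves open. These figures do not model the planned mixed model with imputation.

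It would be tempting to conclude that the primary outcome is compromised. The documents do not support that. Oral fluid screens are expressly outside the rule, and the self-report component is reached only if weekly surveys count as an assessment battery. Section 10.1 makes that possible, but section 5.1 does not say so.

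**What to change.** Delete the conditional re-inclusion clause in section 5.1 and put a fixed rule in section 9.6, before any outcome data are examined by arm:

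- Name one dataset for the main analysis of each survey outcome. Keeping the plan's own default means in-window batteries only, with out-of-window values treated as missing under the planned multiple imputation. Including all batteries is equally valid if prespecified.
- Report the other dataset as a single sensitivity analysis whatever it shows, and state that it does not replace the main result.
- State whether weekly surveys fall under the two-week rule, since they feed the primary outcome.

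This takes a few sentences and no new data collection. The cost of the in-window choice is that late responses, though observed and reported, do not enter the main estimate and are replaced there by imputed values.
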